10.2.1.3. Study Phases for Concomitant Medication

Study Phase	Definition
Prior	If medication end date is not missing and is before enrollment date
Concomitant	Any medication that is not a prior

NOTES:

- Please refer to [Appendix 5: Reporting Standards for Missing Data](#) for handling of missing and partial dates for concomitant medication. Use the rules in this table if concomitant medication date is completely missing.

10.2.2. Treatment Emergent Flag for Adverse Events

Flag	Definition
Treatment Emergent	

• If AE onset date/time is on or after treatment date/time & on or before the treatment stop date/time with 2 days lag time.
• Study Treatment Date/Time ≤ AE Start Date/Time ≤ Study Treatment Date/Time + 2 days.

10.3. Appendix 3: Data Display Standards & Handling Conventions

10.3.1. Study Treatment & Sub-group Display Descriptors

Treatment Group Descriptions				
Study Part	Treatment Group		Data Displays for Reporting	
	Code	Description	Description	Order [1]
1,2	A	Gepotidacin single dose 1500 mg (Period 1)	Single Dose 1500 mg	2
1,2	B	Matching placebo (Period 1)	Placebo	1
1	C	Gepotidacin two 3000 mg doses given at Hour 0 and Hour 12 (Period 2)	Two 3000 mg Doses 12 h Interval	3
1	D	Two matching placebo doses given at Hour 0 and Hour 12 (Period 2)	Placebo	1
1	E	Gepotidacin Two 3000 mg dose given at Hour 0 and Hour 6 (Period 3)	Two 3000 mg Dose 6 h Interval	4
1	F	Two matching placebo doses given at Hour 0 and Hour 6 (Period 3)	Placebo	1
2	G	Gepotidacin two 3000 mg doses (Period 2; exact dosing interval to be determined after Part 1 is complete)	Two 3000 mg doses 12 h Interval or 6 h Interval [2]	3
2	H	Two matching placebo doses (Period 2; exact dosing interval to be determined after Part 1 is complete)	Placebo	1

NOTES:

- Order represents treatments being presented in TFL, as appropriate.
- In Part 2, exact dosing interval to be determined after Part 1 is complete.

10.3.2. Reporting Process & Standards

Reporting Process
Software

 The currently supported versions of SAS and WinNonlin software will be used.
Analysis Datasets

 Analysis datasets will be created according to CDISC standards (SDTM IG Version 3.2 & ADaM IG Version 1.1). For creation of ADaM datasets (ADCM/ADC1/ADAE), the same version of dictionary datasets will be implemented for conversion from SI to SDTM.
Generation of RTF Files

 RTF files will be generated for all reporting efforts described in the RAP.

Reporting Standards	
General	

 • The current GSK Integrated Data Standards Library (IDSL) will be applied for reporting, unless otherwise stated: 
 ○ 4.03 to 4.23: General Principles ○ 5.01 to 5.08: Principles Related to Data Listings ○ 6.01 to 6.11: Principles Related to Summary Tables ○ 7.01 to 7.13: Principles Related to Graphics 	
Formats	

 • All data will be reported according to the actual treatment the subject received unless otherwise stated. • GSK IDSL Statistical Principles (5.03 & 6.06.3) for decimal places (DP's) will be adopted for reporting of data based on the raw data collected. • Numeric data will be reported at the precision collected on the eCRF. • The reported precision from non eCRF sources will follow the IDSL statistical principles but may be adjusted to a clinically interpretable number of DP's. 	
Planned and Actual Time	

 • Reporting for tables, figures and formal statistical analyses : 
 ○ Planned time relative to dosing will be used in figures (with the exception of individual PK concentration-time figures, where actual relative time will be used), summaries, statistical analyses and calculation of any derived parameters, unless otherwise stated. ○ The impact of any major deviation from the planned assessment times and/or scheduled visit days on the analyses and interpretation of the results will be assessed as appropriate. • Reporting for Data Listings: 
 ○ Planned and actual time relative to study drug dosing will be shown in listings (Refer to IDSL Statistical Principle 5.05.1). ○ Unscheduled or unplanned readings will be presented within the subject's listings. ○ Visits outside the protocol defined time-windows (i.e. recorded as protocol deviations) will be included in listings but omitted from figures (mean figures only for PK concentrations), summaries and statistical analyses. 	
Unscheduled Visits	

 • Unscheduled visits will be considered when calculating baseline and in Table 2.9 and Table 2.10, but will not be included in any other summary tables. • Unscheduled visits will not be included in figures. • All unscheduled visits will be included in listings. 	
Descriptive Summary Statistics	
Continuous Data	Refer to IDSL Statistical Principle 6.06.1
Categorical Data	N, n, frequency, %
Graphical Displays	

 • Refer to IDSL Statistical Principals 7.01 to 7.13. 	

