5. CONSIDERATIONS FOR DATA ANALYSES AND DATA HANDLING CONVENTIONS

5.1. Baseline Definitions

For all endpoints (except as noted in baseline definitions) the baseline value will be the last available assessment prior to time of study drug administration, unless noted otherwise.

Parameter	Study Assessments Considered as Baseline				Baseline Used in Data Display
	Screening	Day - 1	Day 1 (Pre-Dose) for Part 1 Period 1 and Part 2 all Periods	Day 5 (Pre-Dose) and Day 9 (Pre-Dose) for Part 1 Period 2 and 3	
Safety					
Hematology	X	X			Day -1
Chemistry	X	X			Day -1
Routine Urinalysis	X	X			Day -1
12-Lead ECG	X	X	X	X	Day 1, Day 5 and Day 9 Pre-Dose
Vital Signs	X	X	X	X	Day 1, Day 5 and Day 9 Pre-Dose

NOTES: unless otherwise stated, the mean of replicate assessments at any given time point will be used as the value for that time point.

If baseline data of ECG or Vital Signs is missing, substitute missing data with the Day -1 or the last non-missing baseline value, whichever date/time is closer to the reference date/time.

For any other assessment, if baseline data is missing no derivation will be performed and baseline will be set to missing, unless otherwise stated.

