10.10.5. Safety Tables

Safety Tables					
No.	Population	IDSL / TST ID / Example Shell	Title	Programming Notes	Deliverable [Priority]
Adverse Events					
2.1	Safety	AE5B	Summary of Adverse Events by System Organ Class and Preferred Term and Maximum Grade		SAC [1]
2.2	Safety	AE5B	Summary of Drug- Related Adverse Events by System Organ Class and Preferred Term and Maximum Grade		SAC [1]
2.3	Safety	AE15	Summary of Common (>=5%) Non-serious Adverse Events by System Organ Class and Preferred Term (Number of Subjects and Occurrences)		SAC [1]
2.4	Safety	AE16	Summary of Serious Adverse Events by System Organ Class and Preferred Term (Number of Subjects and Occurrences)		SAC [1]
2.5	Safety	AE5B	Summary of Acetylcholinesterase-Inhibition Adverse Events of Special Interest by System Organ Class and Preferred Term and Maximum Grade		SAC[1]
2.6	Safety	SAFE_T1	Summary of Cumulative Grades of Acetylcholinesterase-Inhibition Adverse Events of Special Interest		SAC [1]
Laboratory Measurements					
2.7	Safety	LB1	Summary of Chemistry Change from Baseline		SAC [1]
2.8	Safety	LB1	Summary of Hematology Change from Baseline		SAC [1]
2.9	Safety	UR3	Summary of Urinalysis Dipstick Results		SAC [1]
2.10	Safety	LIVER1	Summary of Liver Monitoring/Stopping Event Reporting		SAC [1]
Electrocardiograms					
2.11	Safety	EG1	Summary of ECG Findings		SAC [1]

2.12	Safety	SAFE_T2	Summary of Frequency of Maximum Post-Dose ECG Parameter Corrected QTc Interval		SAC [1]
2.13	Safety	SAFE_T3	Summary of Frequency of Maximum Change from Baseline for ECG Parameter Corrected QTc Interval		SAC [1]
2.14	Safety	EG2	Summary of Change from Baseline in ECG Values		SAC [1]
Vital Signs					
2.15	Safety	VS1	Summary of Change from Baseline in Vital Signs		SAC [1]
Cardiovascular Risk Factors					
2.16	Safety	FH1	Summary of Family History of Cardiovascular Risk Factors		SAC [1]
2.17	Safety	SU1	Summary of Substance Use		SAC [1]

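### As written, SAP 10.3.2 can keep an unscheduled post-dose ECG out of the maximum-QTc tables (2.12 and 2.13), even when it is the participant's worst value

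*SAP*

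**What the plan says.** SAP 10.3.2, under Unscheduled Visits, states that such visits are "considered when calculating baseline and in Table 2.9 and Table 2.10, but will not be included in any other summary tables". SAP 10.10.5 identifies the tables concerned:

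- Table 2.9, exempt: "Summary of Urinalysis Dipstick Results"
- Table 2.10, exempt: "Summary of Liver Monitoring/Stopping Event Reporting"
- Table 2.12, not exempt: "Summary of Frequency of Maximum Post-Dose ECG Parameter Corrected QTc Interval"
- Table 2.13, not exempt: "Summary of Frequency of Maximum Change from Baseline for ECG Parameter Corrected QTc Interval"

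The programming notes for 2.12 and 2.13 are blank. For listings, 10.3.2 says "All unscheduled visits will be included in listings". A separate listings bullet uses a different term: "Unscheduled or unplanned readings will be presented" within the participant's listings. Another bullet in 10.3.2 leaves visits outside the protocol windows out of summaries. On repeats, SAP 5.1 says "the mean of replicate assessments at any given time point will be used as the value for that time point", and 10.4.1 likewise averages several measurements at one analysis time point.

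In the protocol, scheduled ECGs after dosing are single, with triplicates at Day -1 and predose (section 1.3). Section 7.1.2 bases QTc withdrawal on triplicate readings, though it also allows single or averaged values. Section 8.2.3 foresees that extra QTc readings may be needed.

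**The concern.** A table of maxima is read as the worst value observed. Extra ECGs tend to be taken because a participant has symptoms or a QTc looks high, so they are among the readings most likely to be that worst value. The SAP lets unscheduled values set the baseline and enter the liver-event table, but not supply the post-dose QTc maximum. Table 2.13 could thus subtract an unscheduled baseline while ignoring an unscheduled peak.

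QT prolongation is a named risk in protocol 2.3.1, and 12-lead ECG readings are a primary safety endpoint in both parts. At stake is whether two summary tables in the study report show the highest QTc and the largest QTc change that were recorded.

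**Working it through.** The plan gives no figure to reproduce. The check sets the texts side by side and then gives the scale.

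**1. Does anything override the exclusion?** I looked at every SAP section that bears on ECG values.

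- 5.1 covers baseline and the averaging of replicates.
- 8.4 refers to sponsor standards that are not in the text and gives no rule for unscheduled ECGs.
- 10.4.1 covers multiple measurements.
- 10.4.3 derives RR and QTc.
- 10.5.1 puts planned data of withdrawn participants into summaries, which fits the exclusion.
- 10.6.1 says QTc events count under either correction formula, which is a different matter.

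None of them brings unscheduled ECGs into 2.12 or 2.13. The shells SAFE_T2 and SAFE_T3 are not in the text.

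**2. What happens to an extra ECG taken in the clinic?** Part 1 participants are confined from Day -1 to Day 11, and Part 2 participants through each treatment period. An extra ECG may therefore be an added reading on a scheduled day. The SAP leaves at least two routes:

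- It counts as an unscheduled visit and is excluded from 2.12 and 2.13.
- It counts as a repeat at a scheduled time and is averaged under 5.1 and 10.4.1.

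**3. Illustration.** The cut-offs come from SAP 10.6.1: absolute QTc above 450, 480 and 500 msec, and increases above 30 and 60 msec. The readings are invented.

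- Baseline 420, scheduled 490, extra ECG 505. Changes are 490 - 420 = 70 and 505 - 420 = 85, so Table 2.13 shows >60 either way. If the extra ECG is excluded, Table 2.12 shows >480 to 500. If it is averaged, (490 + 505)/2 = 497.5 gives the same band. The recorded worst value is >500.
- Baseline 450, scheduled 505, extra ECG 512. Table 2.12 shows >500 either way. Changes are 505 - 450 = 55 and 512 - 450 = 62. If the extra ECG is excluded, Table 2.13 shows >30 to 60. If it is averaged, (505 + 512)/2 = 508.5, a change of 58.5, gives the same band. The recorded largest change is >60.

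The >500 and >60 criteria coincide only at a baseline of 500 - 60 = 440 msec. Elsewhere a scheduled reading can cross one criterion while only the extra reading crosses the other.

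**4. Scale.** The documents give no rate of unscheduled ECGs. Scheduled post-dose time points in protocol Tables 3, 4 and 5 number 13, 23 and 22. Each part randomizes about 14 to active and 3 to placebo. If all are dosed, one participant in the wrong band moves it by 1/14 = 7.1 points on active, or 1/3 = 33.3 points on placebo in a single period.

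**The case against.** The strongest reply is that little depends on these tables.

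- The Part 2 dosing interval is chosen from data management listings and WinNonlin output (SAP 3.1).
- QTc withdrawal follows protocol 7.1.2, on the ECGs themselves.
- A safety medical monitor follows the data in real time (protocol 6.3), and no hypothesis is tested.
- Listings 37 to 39 cover ECG values and changes of potential clinical importance and, for participants with any such value, all their ECG values. With about 17 participants per part they can be read line by line.
- A clinically significant ECG is also an adverse event.

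All of this stands and limits the consequence. It does not make a table of maxima complete.

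Large excursions may also be rare. Protocol 2.3.1 reports placebo-corrected QTcF increases of 12 to 22 msec after intravenous 1000 and 1800 mg, and protocol 4.3 puts the 1800 mg exposure above that expected here. This makes >60 or >500 unlikely in any one participant but does not exclude outliers.

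It can also be argued that scheduled-only maxima give every participant the same number of chances. That is a legitimate design, but the SAP does not state it as its reason, and it admits unscheduled values to baseline and to the liver-event table.

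Three stronger readings are tempting and are not supported:

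- A reader might infer that the plan certainly drops the worst QTc. That holds only if an in-clinic extra ECG counts as an unscheduled visit, which the SAP leaves open.
- A reader might infer that 2.9 and 2.10 are outdated numbers for the QTc tables, since a dipstick table is an odd choice. The documents do not show this.
- A reader might scale the effect as 1/12 = 8.3 points. Those 12 are PK-evaluable participants, whereas 2.12 and 2.13 use the Safety population.

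**Conclusion.** The point holds as a possibility. Followed as written, SAP 10.3.2 allows Tables 2.12 and 2.13 to leave out an unscheduled post-dose ECG that is a participant's worst value, and the averaging rules could dilute it instead. This rests on the text as available: if the shells already admit such ECGs, 10.3.2 contradicts them and still needs aligning.

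The number affected is unknown and probably small. The effect is 7.1 points per participant on active within a part, assuming all 14 are dosed.

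The documents do not support reading this as a threat to participant monitoring or to the choice of dosing interval. Nor does the eligibility limit of 450 msec bound the cases: it applies to QTcF at entry, while the analysis baseline is renewed at predose on Days 5 and 9 and QTcB is also counted. Severity: minor.

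**What to change.** In SAP 10.3.2:

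1. Verify that 2.9 and 2.10 are the tables intended, before changing either reference.
2. Add Tables 2.12 and 2.13 to the exception. Say that both maxima use scheduled, unscheduled and out-of-window post-dose ECGs, so that the out-of-window bullet does not remove them again.
3. Assign unscheduled ECGs to a treatment by the period and on-treatment window of SAP 10.2.1.1. Keep scheduled ECGs with their own period: the hour-60 ECG in Part 1 Period 3 is 60 - 6 = 54 hours after the second dose, past the two-day limit.
4. State that, for these two tables, an extra ECG near a scheduled time enters as its own reading and a triplicate set enters as its mean, notwithstanding 5.1 and 10.4.1.
5. Footnote the number of unscheduled ECGs per treatment, and check SAFE_T2 and SAFE_T3 against the new text.

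The cost is a few SAP sentences, a footnote and minor programming. No new data are needed and trial conduct does not change. The downside is that maxima then depend slightly on how many extra ECGs a participant had, which the footnote makes visible.

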10.3.3. Reporting Standards for Pharmacokinetics

Pharmacokinetic Concentration Data	
PC Windows Non-Linear (WNL) File	PC WNL file (xpt format) for the non-compartmental analysis will be created according to SOP 314000(2.0). Note: Concentration values will be imputed as per GUI_51487
Descriptive Summary Statistics, Graphical Displays and Listings	Refer to IDSL PK Display Standards. Refer to IDSL Statistical Principle 6.06.1. For continuous data: 
 NQs at the beginning of a participant profile (i.e. before the first incidence of a measurable concentration) are deemed to be zero as it is assumed that in this circumstance no drug is yet measurable in the blood. For NQs at the end of the participant profile (i.e. after the last incidence of a measurable concentration); 
 for individual plots and pharmacokinetic analyses these are dropped (set to missing) as they do not provide any useful information (and can erroneously indicate that absolutely no drug is present) for summary statistics, these are set to 0 (to avoid skewing of the summary statistics) Individual NQs which fall between two measurable concentrations are set to missing (individual values of this nature are assumed to be an anomaly) If two or more NQ values occur in succession between measurable concentrations, the profile will be deemed to have terminated at the last measurable concentration prior to these NQs. For the purpose of individual participant plots, these NQs will be set to 0, and the subsequent measurable concentrations will be retained. For the derivation of pharmacokinetic parameters, these NQs and any subsequent measurable concentrations will be omitted (set to missing). Note: Concentration values will be imputed as per GUI_51487 for descriptive summary statistics/analysis and summarized graphical displays only.

Pharmacokinetic Parameter Data	
PK Parameter to be Derived by Programmer	The following plasma PK parameters will be derived by the Programmer: Ro Cmax, Ro AUC The following urine PK parameters will be derived by the Programmer: Ae total, Ae(t1-t2), Fe%, CLr
Descriptive Summary Statistics, Graphical Displays and Listings	N, n, arithmetic mean, 95% CI of arithmetic mean, geometric mean, 95% CI of geometric mean, SD, SD of logged data, CV (%), and between-subject geometric coefficient of variation (CVb (%)) will be reported. $CV_b (\%) = \sqrt{(\exp(SD^2) - 1) * 100}$ (SD = SD of Ln-Transformed data)
Parameters Not Being Ln-Transformed	λz, λz lower, λz upper, and λz no. of points.
Parameters Not Being Summarized	λz, λz lower, λz upper, and λz no. of points.
Listings	Include the first point, last point and number of points used in the determination of λz for listings.

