9.2. Sample Size Determination

The PK parameter sample size for this study was based on feasibility; however, justification has been considered. For the 1500 mg single-dose regimen, the closest reference study was BTZ116778, with 1500 mg oral dose (immediate-release capsule) taken in fed state, resulting in a coefficient of variation (CV) for AUC(0-∞) and C_{max} of 21.5% and 40.3% respectively. Precision has been evaluated for a range of plausible sample sizes of 10, 12, and 15 participants exposed to the active dose (see table). The precision of sample size of 12 is deemed sufficient for the primary PK endpoint in this study. With 12 participants, the upper limit of the 95% confidence interval for AUC(0-∞) and C_{max} will be approximately 14.5% and 28.0% above the geometric means, respectively.

There were 2 studies similar to the 3000 mg BID (at 6- or 12-hour intervals) dosing regimen. BTZ114595 studied PK profile after a 3000 mg single dose in the fasted state, with CV for AUC(0-∞) and C_{max} being 31.5% and 36.0%, respectively. BTZ116576 studied the 2-hour postdose concentration following a 3000 mg single dose in the fed state, with CV for the concentration being 42.9%. The estimate of AUC(0-∞) CV was higher after 3000 mg than the 1500 mg dose; however, AUC(0-∞) appeared less variable than C_{max} consistently across doses, indicating that C_{max} should be the main

consideration for precision. Despite slight differences in dosing regimens, both 3000 mg single-dose studies indicated the variability of C_{max} approximately 40%, consistent with that of the 1500 mg single dose. Therefore, sample size justification for the 1500 mg single dose is also applicable for the 3000 mg dose.

	Distance from 95% CI Upper Limit to the Geometric Mean (given numbers of participants exposed to the active dose)		
	n=10	n=12	n=15
AUC (0-∞) CV=21.5%	16.4%	14.5%	12.5%
C _{max} CV=40.3%	32.0%	28.0%	24.0%

CI = confidence interval; CV = coefficient of variation.

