7.1.4. Statistical Analyses / Methods

Details of the planned displays are provided in Section 10: List of Data Displays and will be based on GSK Data Standards and statistical principles.

Unless otherwise specified, endpoints/ variables defined in Section 7.1.1 will be summarized using descriptive statistics, graphically presented (where appropriate) and listed.

Primary plasma PK parameters AUC(0- t), AUC(0-∞) (Period 1), AUC(0-24), AUC(0-48), AUC(0-τ) (Periods 2 and 3), C_{max}, RO AUC (Periods 2 and 3), and RO C_{max} (Periods 2 and 3) will be estimated for gepotidacin. For each of these parameters the following summary statistics will be calculated by Study Part and treatment: median, maximum, minimum, arithmetic mean, SD, 95% confidence interval (CI) for the arithmetic mean, geometric mean, CV on geometric mean, 95% CI for the geometric mean, and SD of logarithmically transformed data.

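### As supplied, the SAP 10.3.3 formula for CVb (%) has the factor 100 under the square root; programmed literally, it would return one tenth of the geometric CV

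*SAP*

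**What the plan says.** Under Pharmacokinetic Parameter Data, SAP 10.3.3 lists the statistics to be shown and says that the "between-subject geometric coefficient of variation (CVb (%)) will be reported". The formula follows as "CV_b (\%) = \sqrt{(\exp(SD^2) - 1) * 100", with the note "SD = SD of Ln-Transformed data". In the text supplied, the root covers both the bracketed term and the multiplier.

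SAP 7.1.4 asks for this statistic for the primary plasma parameters, by study part and treatment. Its list includes "geometric mean, CV on geometric mean, 95% CI for the geometric mean, and SD of logarithmically transformed data". SAP 7.2.4 asks for the same set for the secondary parameters. Neither section repeats the formula.

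Protocol 9.2 shows the scale on which the trial's CVs are expressed. For the 1500 mg reference study it gives a "coefficient of variation (CV) for AUC(0-∞) and C_{max} of 21.5% and 40.3% respectively". With 12 participants, the upper 95% confidence limits "will be approximately 14.5% and 28.0% above the geometric means" for AUC(0-∞) and Cmax respectively.

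**The concern.** A geometric CV in percent is 100 times the square root of exp(SD²) − 1. If the 100 is moved inside the root it becomes a multiplier of 10, so the result carries a percent label but is one tenth of the percentage.

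The study tests no hypothesis (Protocol 9.1, SAP 2.4) and plans no PK analysis beyond summary statistics (SAP 7.1.4.1 and 7.2.4.1). The descriptive tables are therefore the PK result. A geometric CV of about 4% printed beside a much larger arithmetic CV and SD of logs would contradict its neighbours in the same table. It would also not be comparable with the CVs that justified the sample size.

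**Working it through.** **Inputs.** The planning CVs are 21.5% (AUC(0-∞)) and 40.3% (Cmax) at 1500 mg, and 31.5% and 36.0% for the 3000 mg single dose (Protocol 9.2). The stated precision at n = 10, 12 and 15 comes from the table in Protocol 9.2. The CVb formula comes from SAP 10.3.3.

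**Step 1: reproduce the protocol's precision figures.** Take SD of logs = √ln(1 + CV²), which is the inverse of CV = √(exp(SD²) − 1). The distance from the geometric mean to the upper 95% limit is exp(t(0.975, n−1) × SD/√n) − 1.

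- AUC(0-∞): SD = √ln(1 + 0.215²) = 0.2126. At n = 12, exp(2.201 × 0.2126/3.464) − 1 = 14.46%.
- Cmax: SD = √ln(1 + 0.403²) = 0.3879. At n = 12, exp(2.201 × 0.3879/3.464) − 1 = 27.95%.

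| Parameter | n | Protocol | Recomputed |
|---|---|---|---|
| AUC(0-∞) | 10 | 16.4% | 16.42% |
| AUC(0-∞) | 12 | 14.5% | 14.46% |
| AUC(0-∞) | 15 | 12.5% | 12.49% |
| Cmax | 10 | 32.0% | 31.98% |
| Cmax | 12 | 28.0% | 27.95% |
| Cmax | 15 | 24.0% | 23.97% |

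All six agree. Two alternatives do not fit: a normal quantile in place of t gives 12.78% and 24.54% at n = 12, and setting the SD of logs equal to the CV gives 14.64% and 29.18%. The protocol therefore works on the scale CV% = 100 × √(exp(SD²) − 1).

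**Step 2: put the same SDs into both forms.**

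| SD of logs | 100 under the root | 100 outside the root |
|---|---|---|
| 0.2126 | 2.15 | 21.5 |
| 0.3076 | 3.15 | 31.5 |
| 0.3491 | 3.60 | 36.0 |
| 0.3879 | 4.03 | 40.3 |

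The ratio is exactly 10 for any SD, since √(100x) = 10√x.

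**Step 3: check that the two scales are incompatible.** Inverting the form with the 100 inside, SD = √ln(1 + (CV%)²/100). This gives 1.314 for 21.5 and 1.687 for 40.3. The upper limits at n = 12 would then be 130% and 192% above the geometric mean, against the stated 14.5% and 28.0%. Neither document plans that inversion. It shows only that the supplied formula and the protocol's scale cannot both hold.

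**The case against.** The strongest objection is that the point depends on where a root sign ends in text read from PDF by a program. A page showing a root over (exp(SD²) − 1), followed by × 100, would be correct and could have been transcribed this way. The brackets around that term fit either reading. The RR, QTcB and QTcF equations in SAP 10.4.3 came through coherently, which suggests that equation structure was generally kept but does not prove the extent of this root. The protocol check shows which relation the planners used; it cannot show what the SAP page prints. This objection stands, and it makes the point conditional.

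Three further limits also stand.

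- A wrong output needs literal programming. Tables 3.3 and 3.4 refer to a standard shell (PKPT4) that may compute the statistic correctly, and that shell is not available to check.
- SAP 7.2.4 lists Tmax and Tlag among the parameters to be given a geometric CV, but the note to Table 3.3 says not to ln-transform them. The formula therefore does not apply to them there.
- The geometric means, their 95% CIs, the SD of logged data and the arithmetic CV are calculated without it.

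A reader might infer that the reported confidence intervals, the choice of Part 2 dosing interval or later Phase III work would be distorted. The documents do not support this. The intervals are reported directly. The dosing interval is chosen from a review of the Part 1 PK and safety results, using data listings and WinNonlin output (SAP 3.1), with no rule based on CVb. Protocol 4.3 says only that the data should help guide Phase III; it gives CVb no role in that.

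**Conclusion.** The formula as supplied is wrong for a statistic labelled in percent, by a factor of exactly 10, and it conflicts with the scale of Protocol 9.2. This part is algebra.

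Whether any reported number would be wrong rests on two assumptions: that the signed SAP also has the 100 under the root, and that the formula is programmed as written. If both hold, CVb (%) is ten times too small for every ln-transformed PK parameter. If the signed page has the 100 outside the root, no error remains.

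The consequence is limited to one descriptive statistic, which could be recalculated from the SD of logs reported beside it. Severity is minor, and confidence is low to medium until the page is checked. The documents do not support the stronger statement that every CVb in the report will be wrong.

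**What to change.** Check the extent of the root sign in SAP 10.3.3 on the signed page. If the 100 is under the root, or its position is unclear, replace the formula with CVb (%) = 100 × √(exp(SD²) − 1), with SD the SD of the ln-transformed data. Writing the 100 first removes the ambiguity whichever way the page was meant. Confirm that the code behind Tables 3.3 and 3.4 uses this form; an SD of logs of 0.3879 should return 40.3.

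The cost is a page check, at most one corrected line in the SAP, and a code check. Nothing changes in the data, the design or the conduct of the study.
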